# 10.1.2.2 Non-Target Lesions

All other lesions or sites of disease should be identified as non-target lesions and should also be recorded at baseline. Measurements are not required and these lesions should be followed as "present" or "absent".

## 10.1.2.3 Lymph Nodes

Lymph nodes identified as target lesions should always have the actual short axis measurement recorded (measured in the same anatomical plane as the baseline examination), even if the nodes regress to below 10mm on study. This means that when lymph nodes are included as target lesions, the 'sum' of lesions may not be zero even if complete response criteria are met, since a normal lymph node is defined as having a short axis of <10mm. Case report forms or other data collection methods may therefore be designed to have target nodal lesions recorded in a separate section where, in order to qualify for CR, each node must achieve a short axis < 10mm. For PR, SD and PD, the actual short axis measurement of the nodes is to be included in the sum of target lesions.

#### 10.1.3 Baseline Evaluation

Baseline disease status should be assessed with cross-sectional imaging (CT with contrast preferred) as close as possible to the start of therapy and never more than 28 days before the beginning of therapy. If iodinated contrast dye is contraindicated, an MRI with gadolinium may substitute for the abdomen and pelvis, but a CT chest without contrast must also be performed.

#### **10.1.4 Repeat Evaluations**

Repeat Evaluations are periodic measurements of disease burden must be assessed utilizing the same cross-sectional imaging modalities as baseline. Participants who do not undergo repeat assessments within acceptable time frames will be removed from study and censored at the time of last evaluation.

# 10.1.5 Best Response

- Complete Response (CR): Disappearance of all target and non-target lesions and no evidence of new lesions documented by 2 disease assessments at least 4 weeks apart.
- Partial Response (PR): At least a 30% decrease in the in the longest dimension (LD) of all target lesions, taking as reference the baseline sum LD. There can be no unequivocal progression of non-target lesions and no new lesions. Documentation by 2 disease assessments at least 4 weeks apart is required.
- Progressive Disease (PD): At least a 20% increase in the sum of LD of target lesions, taking as reference the smallest sum LD or the appearance of new lesions within 8 weeks of study entry. In addition to the relative increase of 20%, the sum must also demonstrate an absolute increase of at least 5 mm.
- Stable Disease (SD): Any condition not meeting the above criteria.
- Inevaluable for response is defined as having no repeat tumor assessments following initiation of study therapy for reasons unrelated to symptoms or signs of disease.

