	dimension (LD) of all target lesions, taking as reference the baseline sum LD. There can be no unequivocal progression of non-target			
	lesions and no new lesions. Documentation by 2 disease assessments			
	at least 4 weeks apart is required. Progressive Disease (PD): At least			
	a 20% increase in the sum of LD of target lesions, taking as reference			
	the smallest sum LD or the appearance of new lesions within 8 weeks			
	of study entry. In addition to the relative increase of 20%, the sum			
	must also demonstrate an absolute increase of at least 5 mm.			
	Stable Disease (SD): Any condition not meeting the above criteria.			
	Inevaluable for response is defined as having no repeat tumor			
	assessments following initiation of study therapy for reasons			
	unrelated to symptoms or signs of disease.			
	Outcome will be assessed as follows:			
	Objective Response Rate (ORR): The proportion of participants with			
	either (1) CR or (2) PR by RECIST 1.1 criteria.			
	Survival: The observed length of life from first dose of study drug to			
	death or the date of last contact.			
	Time to treatment failure: Is defined as the time from first study drug			
	treatment until the participant is started on another line of systemic			
	therapy or participant death, whichever occurs first. Participants who			

are alive and do not start another therapy will be censored at the time of last follow-up.

ety: Safety assessments (vital signs, physical examinations,

Safety: Safety assessments (vital signs, physical examinations, performance status, height/weight, electrocardiogram (ECG) recording, adverse events (AEs), clinical laboratory results (routine hematology and biochemistry, and CT and magnetic resonance imaging [MRI] scans) are to be performed at protocol-specified visits.

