**Table 3: Schedule of Assessments** 

	Baseline/ Screening a	Cycle 1 b	Cycle 2	Cycle 3	Cycle 4	Follow-up Visit 1 and 2 d	Additional Follow-up Visits e	Early Termination Visit f
Obtain Informed Consent	X							
Participant History	X							
Inclusion/Exclusion criteria	X							
Biopsy of Target Lesion c	X	X						
Prior/concomitant medications	Collected from Screening to Follow-up							
Physical Examination	X	X	X	X	X	X		X
Performance status	X	X	X	X	X	X		X
Height/Weight	X	X	X	X	X	X		X
Vital Signs	X	X	X	X	X	X		X
Complete Blood Count	X	X	X	X	X	X		X
Complete Metabolic Panel, LDH	X	X	X	X	X	X		X
Thyroid function testing g	X	X	X	X	X	X		X
Pregnancy test (serum)	X	X	X	X	X	X		X
HCV, HBV, HIV Testing	X							
CT scan h	X				X	X		X
MRI Brain	X							
ECG	X							
Adverse Events	Collected from consent to 100 days after drug discontinuation							
Drug Administration		X	X	X	X			
Research blood (~40mL)	X	X	X	X	X	X		X

PD-L1 expression on banked tumor specimen if available	X					
Survival Data				X	X	X

<sup>aScreening assessments are recommended to be performed within 28 days prior to treatment unless otherwise specified above

<sup>bEach cycle=21 days±4 days

<sup>cBiopsy at baseline for all participants within 14 days of Cycle 1, Day 1. On-treatment biopsy must be performed within 14 days±5 days of first dose of study drug.

<sup>dFollow up period begins when the last dose of study therapy is administered. Follow-up visit 1=21 days from last dose  $\pm$  7 days. Follow-up visit 2=42 days from last dose  $\pm$  7 days. If the participant completed follow-up visit 1 and follow-up visit 2 and *has* progressed, the participant is not required to have scans every 12 weeks. Survival could be assessed via calls every 3 months ( $\pm$ 7 days). If a participant is off treatment and *has not* progressed, they would continue to visit the site and have scans every 12 weeks.

 $^{\rm e}$ Additional follow-up visits will be scheduled every 3 months  $\pm 7$  days. For participants who end treatment for toxicity, scans should continue every 12 weeks until progression of disease. After progression of disease, survival calls will occur every 3 months ( $\pm 7$  days).

<sup>fFor participants who terminate the study early, follow-up will begin 21 days from the last dose (follow-up visit 1).

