<sup>gTSH will be checked at every visit and will reflex to check free T4 if abnormal.

<sup>hPer standard of care to provide data for RECIST measurements as appropriate for each participant per the investigator physician. CT scans will be performed at baseline (-7 days), Week 12, Week 18, and every 12 weeks (±7 days) thereafter until progression of disease, death, or end of study for up to 2 years. A CT scan of the chest, abdomen and pelvis or an MRI of the abdomen and pelvis plus a non-contrast CT of the chest are acceptable.

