Criteria for Evaluation:	
Efficacy: Therapeutic response and outcome assessment will be done in this study using the international criteria proposed by the RECIST version 1.1 Committee. Changes in only the largest diameter (unidimensional measurement) of the tumor lesions are used in the RECIST criteria. Lesions are either measurable or non-measurable. "Target" and "Non-Target" lesions will be identified and recorded at baseline. Responses will be assessed as follows:
 
 • Complete Response (CR): Disappearance of all target and non-target lesions and no evidence of new lesions documented by 2 disease assessments at least 4 weeks apart. • Partial Response (PR): At least a 30% decrease in the in the longest dimension (LD) of all target lesions, taking as reference the baseline sum LD. There can be no unequivocal progression of non-target lesions and no new lesions. Documentation by 2 disease assessments at least 4 weeks apart is required. • Progressive Disease (PD): At least a 20% increase in the sum of LD of target lesions, taking as reference the smallest sum LD or the appearance of new lesions within 8 weeks of study entry. In addition to the relative increase of 20%, the sum must also demonstrate an absolute increase of at least 5 mm. • Stable Disease (SD): Any condition not meeting the above criteria. • Inevaluable for response is defined as having no repeat tumor assessments following initiation of study therapy for reasons unrelated to symptoms or signs of disease. 
Outcome will be assessed as follows:
 
 • Objective Response Rate (ORR): The proportion of participants with either (1) CR or (2) PR by RECIST 1.1 criteria. • Survival: The observed length of life from first dose of study drug to death or the date of last contact. • Time to treatment failure: Is defined as the time from first study drug treatment until the participant is started on another line of systemic therapy or participant death, whichever occurs first. Participants who

	
are alive and do not start another therapy will be censored at the time of last follow-up.
 
Safety: Safety assessments (vital signs, physical examinations, performance status, height/weight, electrocardiogram (ECG) recording, adverse events (AEs), clinical laboratory results (routine hematology and biochemistry, and CT and magnetic resonance imaging [MRI] scans) are to be performed at protocol-specified visits.

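### As written, the progression rule omits new lesions after 8 weeks and all non-target growth, so such progression first seen at Week 12 counts as disease control

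*Protocol*

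**What the plan says.** Protocol 10.1.5 (Best Response) defines PD by a rise in the target-lesion sum of at least 20% and at least 5 mm, or by new lesions within a fixed period: "taking as reference the smallest sum LD or the appearance of new lesions within 8 weeks of study entry". It gives no PD route for non-target lesions. SD is the residual category: "Stable Disease (SD): Any condition not meeting the above criteria". The same section bars complete response (CR) when there is a new lesion ("no evidence of new lesions documented by 2 disease assessments at least 4 weeks apart"). It bars partial response (PR) for both kinds of event: "There can be no unequivocal progression of non-target lesions and no new lesions". Neither bar has a cut-off date.

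The PD wording is repeated in the protocol synopsis under Criteria for Evaluation ("the smallest sum LD or the appearance of new lesions within 8 weeks") and in SAP Appendix 8.1 ("the appearance of new lesions within 8 weeks of study entry").

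Table 3, footnote h, sets the imaging schedule: "CT scans will be performed at baseline (-7 days), Week 12, Week 18, and every 12 weeks".

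SAP 5.4.2 defines DCR as the share of participants whose best objective response (BOR) is SD, PR or CR. SD needs an assessment 8 weeks or more after the first dose. DCR is reported at Week 12 and Week 18 with exact 95% intervals and set beside a historical 28.5%. Under SAP 5.4.1 the investigator assigns BOR.

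**The concern.** The period in which a new lesion can count as PD ends before the first fixed-week scan. Non-target growth never counts as PD. Either event, found at Week 12 with a stable target sum, falls into the residual SD category and is reported as disease control.

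This is out of line with the rest of the protocol. The CR and PR bars in the same section treat a new lesion as disqualifying whenever it appears. Inclusion criterion 4 accepts a new measurable lesion as progression with no 8-week limit.

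DCR is a secondary endpoint with 12 participants per arm, so a single misclassified scan is visible in the estimate. SAP 5.4.4 plans no sensitivity analysis that would show the effect. Because the documents also name RECIST 1.1 by reference, an investigator who works from that source and one who works from the printed list could score the same scan differently.

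**Working it through.** **1. The plan's own figures.** SAP Table 1 gives exact 95% intervals for n = 12, and DCR uses the same n and method. The Clopper-Pearson limits are

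- lower = Beta quantile(0.025; x, 12 − x + 1)
- upper = Beta quantile(0.975; x + 1, 12 − x)

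All six rows (1/12 to 6/12) reproduce to 0.1 point.

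**2. Timing (Day 1 = first dose).** Study entry is not defined, so two readings are shown.

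- Entry = first dose: 8 weeks is 56 days, so the clause closes on Day 57. Week 12 is Day 85. Gap: 85 − 57 = 28 days.
- If the Week 12 scan may be 7 days early: Day 78, and 78 − 57 = 21 days. This is an assumption. In footnote h the ±7 days follows the 12-weekly scans, and SAP 5.4.2 gives Week 12 only +7 days.
- Entry = consent, which Protocol 9.2.1.2 allows up to 4 weeks before the first dose: the clause closes 56 − 28 = 28 days after the first dose, on Day 29. Gap: 85 − 29 = 56 days.

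**3. One participant taken through the text.** Suppose the Week 12 scan shows an unchanged target sum and one new lesion.

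| Test | Result |
|---|---|
| CR | Fails: new lesion, and targets persist |
| PR | Fails: no 30% decrease, and a new lesion |
| PD, target sum | Fails: no 20% and 5 mm rise |
| PD, new lesion | Fails: Day 85 is after Day 57 |
| PD, non-target | No such route |
| SD | Met by default |
| SAP 5.4.2 minimum time for SD | Met: Day 85 is at least 8 weeks after first dose |
| Counted in DCR | Yes |

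Unequivocal non-target growth with a stable target sum gives the same result. The SAP minimum time cannot filter these cases out: with entry at or before the first dose, SD starts to qualify no earlier than the new-lesion clause closes.

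DCR is built on BOR, so SD at Week 12 also carries into Week 18. Week 18 adds a new misclassification only for someone with no qualifying SD, PR or CR at Week 12.

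**4. Other scans that might fall inside the window.**

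- Table 3 marks a CT under Cycle 4. Its nominal day is 1 + 3 × 21 = Day 64, also after Day 57. Only if all three intervals run 4 days short is it Day 1 + 3 × 17 = Day 52.
- Table 3 also marks CT at early termination and at follow-up visits 1 and 2. The first is timed as "Follow-up visit 1=21 days from last dose" and the second 42 days from last dose, each ±7 days. Someone stopping after one dose (Day 1) has visits on Days 22 and 43. After two doses (Day 22), they fall on Days 43 and 64. Such participants can be scanned in time for the clause to apply.

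**5. Size.** The documents do not give the number affected. For an assumed k of 12, DCR rises by k/12. Starting from a true 3/12:

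| k | Reported DCR | Exact 95% CI |
|---|---|---|
| 0 | 3/12 = 25.0% | 5.5 to 57.2 |
| 1 | 4/12 = 33.3% | 9.9 to 65.1 |
| 2 | 5/12 = 41.7% | 15.2 to 72.3 |
| 3 | 6/12 = 50.0% | 21.1 to 78.9 |

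The benchmark is 0.285 × 12 = 3.42 participants, so one added participant crosses it from 3/12 and from no other count. All four intervals contain 28.5%.

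As a second illustration, assume the true DCR is 28.5% and a share f of the remaining 71.5% progress only by these routes. Expected reported DCR = 0.285 + 0.715f, which is 35.6% at f = 0.1, 42.8% at 0.2 and 49.9% at 0.3. That is 0.86, 1.72 and 2.57 extra participants per 12.

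**The case against.** The strongest reply is that RECIST v1.1, not the printed list, governs. Protocol section 12 and SAP section 2 say the SAP supersedes the protocol, and SAP 3.3.2 and 5.4.2 name RECIST v1.1 for DCR and SD. SAP Appendix 8.1 only reproduces the protocol synopsis, including the two-stage design text that SAP 3.4 calls incorrect, so it is weak evidence of the operative rule. The analysed BOR is also the investigator's call.

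This shows that misclassification is conditional, and that part stands. It does not settle which rule applies. The protocol prints its list under the RECIST 1.1 name, both in section 10.1 and in the synopsis. The SAP body has no PD rule. SAP section 6, which corrects other protocol points, is silent here. The documents do not reproduce RECIST v1.1, so the case rests on the mismatch between the PD rule and the CR and PR bars. Strictly, a rule may deny PR for a new lesion and still call the case stable. But then disease control includes participants with new tumours.

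Three further limits stand. The number affected is unknown, and the 3/12 starting point is the one from which a single case crosses the benchmark. The comparison with 28.5% is descriptive, the SAP disclaims hypothesis testing, and no planned decision turns on DCR. Finally, Protocol 10.1.2.2 has non-target lesions followed only as present or absent, so recorded data may not be enough to re-check growth. The PR definition already requires investigators to judge unequivocal non-target progression, so the judgement itself is not new.

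**Conclusion.** The point holds. On the written criteria, a participant whose only progression at the Week 12 scan is a new lesion or non-target growth is SD and counts in DCR at Week 12 and, through BOR, at Week 18. Each such participant raises that arm's DCR by 8.3 points.

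This rests on two assumptions: that the printed list is the one applied, and that study entry is no later than the first dose. The frequency is unknown; the range of 0 to 3 per arm is illustrative.

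ORR is not affected, because CR bars new lesions and PR bars both events at any time. TTF and OS do not use PD. The consequence is limited to one descriptive secondary endpoint, so this should be corrected but does not threaten the primary result.

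**What to change.** - In Protocol 10.1.5, the synopsis and SAP Appendix 8.1, delete the 8-week limit. Define PD to include any new lesion at any time and unequivocal progression of non-target lesions. PD then matches the CR and PR bars, and one definition stands under the RECIST v1.1 name.
- In SAP 5.4.1 and 5.4.2, state that this definition governs BOR and DCR. This is the essential step even if conduct is already far advanced.
- List the change in SAP section 6.

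Do this before database lock, since SAP section 2 allows no change from then on.

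The cost is wording, with no added visits or scans. Reported DCR may be lower than under the literal text. Any SD already recorded under the printed list needs checking against the scan data; for non-target lesions that may mean going back to the images or reports. Progression also ends the 12-weekly scans in Table 3, so the protocol wording should be checked there for consistency. Section 7.3 already refers to RECIST 1.1 for radiologic progression, and this change sets no treatment rule.

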# **10.2** Quantifying Clinical Correlates of Response

Outcome will be assessed as follows:

- Objective Response Rate (ORR): The proportion of participants with either (1) CR or (2) PR by RECIST 1.1 criteria.
- Survival: The observed length of life from first dose of study drug to death or the date of last contact
- TTF: Is defined as the time from first study drug treatment until the participant is started on another line of systemic therapy or participant death, whichever occurs first. Participants who are alive and do not start another therapy will be censored at the time of last follow-up.

## 11 SAFETY ASSESSMENTS

Safety assessments (vital signs, physical examinations, performance status, height/weight, ECG recording, AEs, clinical laboratory results (routine hematology and biochemistry, and CT and MRI scans) are to be performed at protocol specified visits, as specified in the Schedule of Assessments, Table 3.

#### 11.1 Adverse Events

## 11.1.1 Definition of Non-serious Adverse Events

An AE is defined as any new untoward medical occurrence or worsening of a preexisting medical condition in a clinical investigation participant administered an investigational (medicinal) product and that does not necessarily have a causal relationship with this treatment. An AE can therefore be any unfavorable and unintended sign (such as an abnormal laboratory finding), symptom, or disease temporally associated with the use of investigational product, whether or not considered related to the investigational product.

A non-serious AE is an AE not classified as serious.

The collection of non-serious AE information will begin at initiation of study drug. All non-serious AEs (not only those deemed to be treatment-related) should be collected continuously during the treatment period and for a minimum of 100 days following the last dose of study treatment.

Non-serious AEs should be followed to resolution or stabilization, or reported as SAEs if they become serious. Follow-up is also required for non-serious AEs that cause interruption or discontinuation of study drug and for those present at the end of study treatment as appropriate.

The causal relationship to study drug is determined by a physician and should be used to assess all AE. The casual relationship can be one of the following:

**UNRELATED**: This category applies to those AEs that are clearly and incontrovertibly due to extraneous causes (disease, environment, etc.).

**UNLIKELY**: This category applies to those AEs that are judged to be unrelated to the test drug, but for which no extraneous cause may be found. An AE may be considered unlikely to be related to study drug if or when it meets 2 of the following criteria: (1) it does not follow a reasonable temporal sequence from administration of the test drug; (2) it could readily have been produced by the subject's clinical state, environmental or toxic factors, or other modes of therapy administered to the subject; (3) it does not follow a known pattern of response to the test drug; or (4) it does not reappear or worsen when the drug is readministered.

**POSSIBLY**: This category applies to those AEs for which a connection with the test drug administration appears unlikely but cannot be ruled out with certainty. An AE may be considered possibly related if or when it meets 2 of the following criteria: (1) it follows a reasonable temporal sequence from administration of the drug; (2) it could not readily have been produced by the subject's clinical state, environmental or toxic factors, or other modes of therapy administered to the subject; or (3) it follows a known pattern of response to the test drug.

**PROBABLY**: This category applies to those AEs that the investigator feels with a high degree of certainty are related to the test drug. An AE may be considered probably related if or when it meets 3 of the following criteria: (1) it follows a reasonable temporal sequence from administration of the drug; (2) it could not be reasonably explained by the known characteristics of the subject's clinical state, environmental or toxic factors, or other modes of therapy administered to the subject; (3) it disappears or decreases on cessation or reduction in dose (note that there are exceptions when an AE does not disappear upon discontinuation of the drug, yet drug-relatedness clearly exists; for example, as in bone marrow depression, fixed drug eruptions, or tardive dyskinesia); or (4) it follows a known pattern of response to the test drug.

**DEFINITELY**: This category applies to those AEs that the investigator feels are incontrovertibly related to test drug. An AE may be assigned an attribution of definitely related if or when it meets all of the following criteria: (1) it follows a reasonable temporal sequence from administration of the drug; (2) it could not be reasonably explained by the known characteristics of the subject's clinical state, environmental or toxic factors, or other modes of therapy administered to the subject; (3) it disappears or decreases on cessation or reduction in dose and recurs with re-exposure to drug (if rechallenge occurs); and (4) it follows a known pattern of response to the test drug.

Classification of AEs by intensity should also be determined by a physician.

Adverse events can be spontaneously reported or elicited during open-ended questioning, examination, or evaluation of a participant. (In order to prevent reporting bias, participants should not be questioned regarding the specific occurrence of one or more AEs).

